12.1. Data Collection

The visit and data collection schedule for the REDUCE-HTN: REINFORCE Study is provided in Table 12.1-1. Subjects may be followed for up to 36 months but are only required to complete follow up through the 24 month visit.

Table 12.1-1: REDUCE-HTN: REINFORCE Study Data Collection for Scheduled Visits

	Screening / Baseline	RDN and Masked Procedure	Hospital Discharge	2 Wks (14±7 days)	4 Wks (28±7 days)	8 Wks (56 ±7 days)	3 Mon (90 ±14 days)	4 Mon (120 ±14 days)	5 Mon (150 ±14 days)	6 Mon (180 ±14 days)	12 Mon (365 ±30 days)	18 Mon (540 ±30 days)	24 Mon (730 ±30 days)	30 Mon (900 ±30 days)	36 Mon (1095 ±30 days)
Office Seated BP x 3; Standing BP; Heart Rate; Height & Weight; Limited Physical Exam	X		X	X	X	X	X	X	X	X	X	X	X	X ³	X ³
24-hour Ambulatory BP	X				X	X				X	X				
Quality of Life (PGWBI)	X					X				X	X		X		X ³
Renin ²	X					X				X					
Aldosterone ²	X					X				X					
Serum Creatinine	X		X			X				X	X		X		X ³
CBC with platelets, BMP, HbA1c	X		X			X				X	X		X		X ³
Pregnancy Test (as applicable)	X	X													
CTA	X									X ¹			X ⁴		
Renal Angiogram (DSA)		X								X ¹			X ⁴		
Renal Duplex Ultrasound (DUS)										X			X ⁴		
Adverse events assessment		X	X	X	X	X	X	X	X	X	X	X	X	X ³	X ³
Blinding Index Assessment			X			X				X					

¹ A Renal DUS is required for subjects who receive treatment. If DUS shows a ≥60% stenosis per the core laboratory or is inconclusive per the core laboratory after repeat DUS, CTA or DSA are required.

² Renin and Aldosterone Serum tests will be collected at screening/baseline, 8 weeks and 6 months post-randomization. Subjects that are enrolled/randomized prior to the implementation of protocol version AB will not undergo Renin or Aldosterone testing

³ Visit/assessment not required after approval of protocol version AH.

⁴ Only subjects who received treatment and reach the 24 month follow up after approval of protocol version AH will be required to undergo a DUS at 24 months. If the DUS shows a ≥60% stenosis per the core laboratory or is inconclusive per the core laboratory after repeat DUS, a CTA or DSA is required.

12.1.1. Medical Equipment Description

12.1.1.1. Office-based Blood Pressure Monitoring

Office-based blood pressure (OBP) measurements will be collected during screening, at hospital discharge and each study follow-up visit with an automatic oscillometric Omron HEM-705CP-II monitor (Omron Healthcare, Vernon Hills, IL, USA) with a printer for documentation. Blood pressure will be measured according to the Standard Joint National Committee VII²⁶ and the European Society of Cardiology and European Society of Hypertension²⁷ recommendations. The devices should be properly maintained and regularly calibrated according to the manufacturer's recommendations.

Office-based blood pressure must be obtained by study personnel that are blinded to treatment assignment through the 6-month follow-up visit. Site blinding guidelines are described in the Manual of Operations.

Refer to the instruction manual for the OBP monitor for set up and care information, and instructions for preparing the subject for blood pressure (BP) measurements, applying the BP cuff, taking the BP measurements and using the monitor in special conditions (i.e., SBP >220mmHg).

NOTE: A properly sized BP cuff should be selected based upon the subject's arm circumference.

During subject preparation the subject should:

- avoid smoking, eating or vigorous exercise for 30 minutes prior to the BP measurements
- sit quietly for 5 minutes prior to the measurements
- sit in a chair with feet flat on the floor
- rest arm on a table so that the cuff is at the same level as the heart
- avoid talking during the measurements

NOTE: The BP should be measured in both upper arms at the screening visit to detect possible differences in the measurements. The arm with the higher values should be used for baseline and all subsequent measurements. It is recommended to obtain follow-up BP measurements at the same time of day as the baseline measurements are obtained.

Three (3) BP measurements will be obtained using the same arm at least 2-3 minutes apart during a single visit. The provided monitor must be used for all OBP measurements. If the lowest and highest systolic BP (SBP) measurements are more than 15 mmHg apart, additional readings should be performed. The last 3 consecutive consistent SBP measurements will be averaged to determine the final value to be used to assess eligibility. If the lowest and highest SBP measurements are more than 20 mmHg apart after a total of six measurements, the measurements will not be used to assess study eligibility, but the subject's OBP may be reassessed for study eligibility at a subsequent time point. If the lowest and

highest SBP values remain more than 20 mmHg apart after 6 measurements at a subsequent assessment, the patient will be excluded from the study.

To assess for orthostatic hypotension during screening and follow-up, a standing BP measurement must be obtained within 3 minutes of assuming a standing position using the standardized equipment provided for the study.

NOTE: The heart rate will be recorded at the same time as all blood pressure measurements.

12.1.1.2. 24-Hour Ambulatory Blood Pressure Monitoring

24-hour ambulatory blood pressure monitoring (ABPM) will be performed at screening, the 4 and 8-week, and 6 and 12-month follow-up visits post randomization. A qualified ABPM core laboratory will be utilized. The core laboratory will provide validated ABPM equipment to all study sites.

The ABPM measurements will be collected with the Microlife® Watch BP-03 (Microlife Intellectual Property GMBH, Great Neck, NY, USA) with readings taken as described in ABPM Core Laboratory Manual and overall 24-hour averages calculated for each subject. Minimum acceptance criteria, as described in the Manual of Operations, are required for inclusion of the ABPM data. If the minimum acceptance criteria are not met, the ABPM procedure may be repeated if the study visit window allows.

ABPM data will be transmitted to, reviewed and managed by the core laboratory, and reported to Boston Scientific Corporation (BSC) or delegate for analysis purposes.

The ABP monitor set up, care information, instructions for preparing the subject for ABPM measurements, applying the ABPM cuff, fitting the ABP monitor and transmitting the ABPM data are outlined in the ABPM Core Laboratory Manual.

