6.7. Device Labeling

The Vessix Reduce Catheter Directions for Use (DFU), Operator's Manual (OM) and packaging are labeled as investigational. Use of these devices outside of this clinical study is strictly prohibited. A copy of the DFUs and OM will be provided in the local language and are included in the study Manual of Operations. The catheter packaging will include peelable, self-adhesive labels for each unit shipped. The labeling will include the following information in English.

- Product Name
- Universal Part Number (UPN)
- Serial or tracking identification number
- Lot number
- Product dimensions
- Expiration (use by) date

7. Objectives

The objective of the REDUCE-HTN: REINFORCE Clinical Study is to assess safety and efficacy of the Vessix™ Renal Denervation System for the treatment of uncontrolled hypertension [off-treatment office systolic blood pressure (OSBP) ≥ 150 mmHg and ≤ 180 mmHg].

8. Endpoints

The endpoints of the study are based upon the safety and efficacy of the Vessix Renal Denervation System.

8.1. *Primary Efficacy Assessment*

The primary efficacy assessment is the mean reduction in average 24-hour ambulatory systolic blood pressure (ASBP) at 8 weeks post randomization.

8.2. *Safety Assessments*

Safety Assessments analyzed at all follow-up time points:

- All-cause death
- Renal failure
- Hospitalization for hypertensive crisis
- Hospitalization due to severe hypotension/syncope

Safety Assessments analyzed at 4 weeks:

- Significant embolic event resulting in end-organ damage or intervention to prevent it
- Renal artery dissection or perforation requiring intervention
- Vascular complications requiring surgical repair, interventional procedure, thrombin injection, or blood transfusion

Safety Assessments analyzed at 6 months:

- Significant new renal artery stenosis assessed by duplex ultrasound (DUS) and confirmed by the angiographic core laboratory [$>70\%$ stenosis by computed tomographic angiography (CTA) or digital subtraction angiography (DSA)] through 6 months post randomization
 - Subjects will be required to have a 6-month duplex ultrasound to assess for evidence of significant stenosis, defined as $\geq 60\%$ as reported by the duplex ultrasound (DUS) core laboratory. A significant stenosis ($\geq 60\%$) detected by DUS will trigger the performance of a confirmatory CTA or DSA.
 - If a diagnostic duplex ultrasound cannot be adequately achieved at the 6-month follow-up, then a CTA or DSA must be conducted.

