9.3. Justification for the Study Design

The REDUCE-HTN: REINFORCE Clinical Study is intended to demonstrate the effects of renal denervation in the absence of potentially confounding antihypertensive medications. The design, including an antihypertensive medication wash-out phase, is similar to pharmaceutical study designs looking at early efficacy of compounds. The number of safety events in patients off therapy during the primary efficacy assessment period is low in the pharmaceutical studies.^{23,24}

A masked procedure will be used as the control for this study. Subjects and study personnel obtaining OBP will be blinded to treatment assignment. The primary efficacy endpoint will be evaluated using ABPM which minimizes any placebo effect²⁵. Subject blinding, the blinded blood pressure assessor and the utilization of ABPM will provide unbiased data in support of efficacy.

Because REDUCE-HTN: REINFORCE Clinical Study is the first study to evaluate the Vessix Renal Denervation System in this off medication population, actions will be taken throughout the course of the study to minimize risks to enrolled subjects. These risk minimization efforts are summarized in Section 21.2.

10. Subject Selection

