12.9. Follow-up Visit Week 8 (56 ±7 days)

The 8-week follow-up office visit (56 ±7 days) will include the following assessments:

- 24-Hour Ambulatory BP Monitoring

- Limited physical exam including height and weight
- Quality of Life Assessment
- Blood assays (serum creatinine, CBC and platelets, renin, aldosterone, BMP and HbA1c)
- Office-based sitting and standing blood pressure (obtained by blinded study personnel in the US) and heart rate
- Medications administered since last visit
- Adverse events
- Blinding index assessment

After completion of the 8-week follow-up assessments, subjects not at target (target defined as OSBP <140 mmHg) will have antihypertensive medications reintroduced as described in Section Medication Additions13.

12.10. Follow-up Visits Months 3, 4 and 5 (90 ±14 days, 120 ±14 days, 150 ±14 days)

The 3-month (90 ±14 days), 4-month (120 ±14 days) and 5-month (150 ±14 days) follow-up visits will include the following assessments:

- Limited physical exam including height and weight
- Office-based sitting and standing blood pressure (obtained by blinded study personnel in the US) and heart rate
- Medications administered since last visit
- Adverse events

After completion of the 3, 4 and 5-month OBP follow-up assessments, subjects not at target (target defined as OSBP <140 mmHg) will have antihypertensive medications adjusted or reintroduced as described in Section 13.2.

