14.1. Endpoints

14.1.1. Primary Efficacy Assessment

Due to enrollment termination with approximately half of the planned subjects randomized, the primary efficacy assessment will be observational only. No formal tests of hypotheses will be performed.

The primary efficacy assessment for the study is mean reduction in average 24-hour ASBP through 8 weeks post randomization in subjects treated with renal denervation (Test) and subjects treated with masked procedure (Control).

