14.2. General Statistical Methods

14.2.1. Analysis Sets

The primary and pre-specified additional assessments will be analyzed on an intent-to-treat (ITT) basis and on a per-protocol basis. For the ITT analysis, all subjects who sign the written ICF and are randomized in the study will be included in the analysis population, regardless of whether the subjects receive the assigned treatment. For the per-protocol analysis, only randomized subjects who meet the eligibility criteria and receive the assigned treatment will be included in the analysis population.

The ITT population will be the primary analysis set for the purpose of assessing superiority of Test to Control for 8-week average 24-hour ASBP reduction. All other endpoint analyses will be based on ITT population.

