14.3. Data Analyses

Baseline data will be summarized by treatment group for the randomized study. Subject demographics, clinical history, procedure assessment, and medication compliance will be summarized using descriptive statistics (e.g., mean, standard deviation, n, minimum, maximum) for continuous variables and frequency tables for discrete variables. The analysis unit may be (but will not be limited to) by subject, catheter, or treatment.

Test and Control in the randomized study will be compared as needed with a Chi-square test or a Fisher exact test for discrete variables and a Student t-Test for continuous variables. The differences between Test and Control in the randomized study and their 95% confidence intervals will be presented as needed.

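### As written, a subject without a valid 8-week ABPM adds nothing to the ITT estimate of 8-week ASBP change, while a scheduled week-4 ABPM goes unused

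*Combined protocol and SAP*

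**What the plan says.** **Endpoint.** Section 8.1: "The primary efficacy assessment is the mean reduction in average 24-hour ambulatory systolic blood pressure (ASBP) at 8 weeks post randomization". Section 14.1.1 words it differently, as "mean reduction in average 24-hour ASBP through 8 weeks post randomization", and makes the assessment observational, without a hypothesis test.

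**Who is analysed.** Section 14.2.1: "all subjects who sign the written ICF and are randomized in the study will be included in the analysis population".

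**Which recordings count.** Section 12.1.1.2: "Minimum acceptance criteria, as described in the Manual of Operations, are required for inclusion of the ABPM data". After a failed recording, "the ABPM procedure may be repeated if the study visit window allows". The 8-week window is day 56 ±7, so days 49 to 63.

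**How arms are compared.** Section 14.3 offers, as needed, "a Student t-Test for continuous variables", with differences and 95% confidence intervals. Section 14 has no rule for a missing or rejected ABPM.

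**Week 4.** Table 12.1-1 and sections 12.1.1.2 and 12.8 schedule a 24-hour ABPM at week 4. No assessment in section 8 uses it: ambulatory systolic pressure is assessed at 8 weeks (8.1) and at 6 and 12 months (8.3).

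**Drugs.** Section 9.3 says the study is meant to show "effects of renal denervation in the absence of potentially confounding antihypertensive medications". Sections 12.5 and 13.1 keep subjects off antihypertensive drugs through the primary assessment unless rescue is needed. Section 12.9 times reintroduction thus: "After completion of the 8-week follow-up assessments, subjects not at target". Section 13.2 lets the investigator use 8-week ABPM data in that decision but does not require it.

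**The concern.** An all-randomized set and a single-time-point change score do not fit together without a missing-data rule. A t-test or a difference in mean 8-week change can use only subjects who have an 8-week value. The result would carry the ITT label but rest on observed cases.

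With no hypothesis test, the estimate and its interval are the whole efficacy result, and 51 subjects already make that interval wide. A second ambulatory reading from the intended off-drug period exists for most subjects who lack the 8-week one, and leaving it out discards information. If subjects with high week-4 pressure more often lack an 8-week value, the observed-case difference is also biased.

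A second, smaller gap concerns which recording is the off-drug value. The text does not say whether a recording must be accepted before drugs restart, or how a repeat begun after restart is classified.

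**Working it through.** **The plan's own figures.** The plan gives no expected rate of missing or rejected ABPM and no inputs for its sample size, so neither can be reproduced. The one check available is 51 randomized of up to 100, which is 51% and agrees with the statement in 14.1.1 that about half were randomized.

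**Inputs**
- From the documents: 51 randomized at 2:1, nominally 34 Test and 17 Control (the actual split is not given).
- SD of change 14.4 mmHg, from the earlier single-arm study in section 5.2.1. Those patients were on drugs and measured at 6 months, so using it here is an assumption.
- Assumptions: fraction of 8-week values missing m = 0.10 to 0.20; week-4/week-8 correlation of change ρ = 0.5 to 0.8; drug effect 10 mmHg; true difference 6 mmHg in the simulation.

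**Step 1. Precision with observed cases only.** Half-width = t(0.975, df) × SD × √(1/nT + 1/nC).
- 34:17: 2.010 × 14.4 × 0.2970 = 8.60 mmHg
- 10% missing, 31:15 (46 subjects): 2.015 × 14.4 × 0.3145 = 9.13 mmHg, 6.2% wider
- 20% missing, 27:14 (41 subjects): 2.023 × 14.4 × 0.3293 = 9.59 mmHg, 11.6% wider

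**Step 2. What week 4 recovers.** Relative to full data, the variance is 1/(1−m) for observed cases and (1−ρ²)/(1−m) + ρ² for a likelihood estimate using week 4. The ratio of the second to the first is 1 − ρ²m. The interval narrows by 1 − √(1 − ρ²m).

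| m | ρ | Variance reduction ρ²m | Interval narrower by |
|---|---|---|---|
| 0.10 | 0.5 | 2.5% | 1.3% |
| 0.10 | 0.8 | 6.4% | 3.3% |
| 0.20 | 0.5 | 5.0% | 2.5% |
| 0.20 | 0.8 | 12.8% | 6.6% |

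A simulation (8,000 replicates per setting, 34:17, SD 14.4) agrees. With values missing completely at random, the variance ratio is 1.02 to 1.16, a reduction of 1 − 1/1.02 = 2% to 1 − 1/1.16 = 14%. In mmHg the gain is small: 1.3% of 9.13 is about 0.1, and 6.6% of 9.59 is about 0.6.

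**Step 3. Bias from missing values.** If missing subjects' change differs from that of observed subjects by d, the Test−Control difference is shifted by d × (mC − mT). For d = 10 mmHg, 20% missing in Control and 10% in Test give 10 × 0.10 = 1.0 mmHg toward zero; equal rates give 0. When the simulation makes missingness rise with the week-4 value, with a true difference of −6 mmHg, the observed-case estimate is off by +0.21 to +0.52 mmHg (toward zero) and the week-4-informed estimate by −0.02 to +0.14 mmHg. The size depends on the imposed strength of that dependence, which is not in the documents.

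**Step 4. On-drug repeats.** Shift = drug effect × (share of Control affected − share of Test affected). At 10 mmHg:
- one Control subject: 10/17 = 0.59 mmHg toward zero
- one Test subject: 10/34 = 0.29 mmHg the other way
- 5% of Test and 20% of Control: 10 × 0.15 = 1.5 mmHg toward zero
- equal shares: 0

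**The case against.** The strongest reply is that the plan nowhere prescribes complete-case analysis. Section 14.3 offers the t-test as needed and does not assign it to the primary; 14.1.1 makes that assessment observational. Sections 14.3.2 and 14.3.5 refer to a Statistical Analysis Plan whose separate text is not in the supplied document and may hold a missing-data rule. This stands: the observed-case result is inferred from silence together with the only tools named. It does not remove the need for a rule in the section that defines the ITT set.

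Three stronger readings are tempting, and the documents do not support them.

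- *The plan permits an on-drug repeat to count as the primary value.* It does not say so. Sections 12.5 and 13.1 keep subjects off drugs through the primary assessment, and 12.9 lists ABPM among the assessments to be completed before drugs are reintroduced. That can be read as requiring a valid recording first. It can also be read as completion of the visit, since 12.1.1.2 allows a repeat within the window and says nothing about when acceptance is decided. This is an ambiguity, not a permission.
- *The estimate is biased toward zero.* No passage links high pressure to a missing or rejected recording, and drugs are reintroduced in both arms. Missing values with the same d in both arms, or on-drug repeats, bias the difference toward zero only if they are more common in Control. That is plausible if the device works, but it is not shown.
- *Every week-4 value is off drug.* Rescue is possible before week 4, so some may not be.

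It is also fair that the gain is small against a half-width of about 9 mmHg, and that a repeated-measures model is one reasonable choice among several.

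**Conclusion.** The point holds as a gap in estimation. The supplied text leaves subjects without a valid 8-week ABPM out of the nominal ITT estimate in effect and gives the week-4 ABPM no role. Under the stated assumptions, using week 4 reduces the variance by about 2-14% and the interval width by about 1-7%. If missingness depended on week-4 pressure, it would remove most of a 0.2-0.5 mmHg attenuation. These sizes rest on assumed missing rates, correlations, SD and mechanism, and on a nominal 34:17 split. Week 4 does not cure missingness that depends on the unseen 8-week value, and a subject with no valid post-baseline ABPM still contributes nothing.

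With no test planned, type I error and power are not at issue. The change is worth making because it is cheap and the estimate is all the trial will report on efficacy; its absence does not invalidate the trial.

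**What to change.** In sections 14.1.1 and 14.3:

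1. Estimate the 8-week Test−Control difference and its 95% confidence interval, descriptively, from a mixed model for repeated measures on week-4 and week-8 24-hour ASBP. Include arm by visit and an unstructured covariance, with baseline ASBP as a covariate or with baseline means constrained equal between arms. An unconstrained baseline in the outcome vector would give no baseline adjustment. Use all randomized subjects with a valid post-baseline ABPM.
2. Flag values recorded after rescue, at week 4 as well as week 8.
3. Tabulate valid, rejected and missing 8-week recordings by arm.
4. As a data-classification rule only, report 8-week recordings that began after antihypertensive drugs were reintroduced separately from the off-drug primary value.
5. Reconcile sections 12.1.1.2, 12.9 and 13.2 on the order of accepted ABPM and drug restart, and align *at* 8 weeks (8.1) with *through* 8 weeks (14.1.1). No clinical rule is proposed.

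The cost is wording, modest programming and reliance on a missing-at-random assumption, which should be stated. The ABPM data are already scheduled. Sections 12.8 and 12.9 collect medications since the last visit, but the sponsor should confirm that start dates are recorded precisely enough for items 2 and 4. Section 14.3.5 already provides for an amended plan approved before analysis.

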12.2. Study Candidate Screening

Subjects will be pre-screened for participation in the study through a review of medical records and attainment of clinical data to support the eligibility criteria (inclusion and exclusion criteria) through normal standard of care procedures.

12.3. Informed Consent

All subjects who appear to meet the eligibility criteria based on pre-screening will have the study explained to them. They will be provided a copy of the written informed consent form (ICF) and extended an invitation to sign the form to allow further assessments to be conducted to determine their eligibility to participate in the study.

Study personnel should explain to the subject that even if the subject agrees to participate in the study and signs the ICF, screening assessments prior to randomization/enrollment, including the diagnostic angiogram, may demonstrate that the subject is not a suitable candidate for the study.

